## 11.3. Appendix 3: Study Phases and Treatment Emergent Adverse Events

### 11.3.1. Study Phases

All assessments and events (including those collected as planned, early withdrawal and unscheduled visits) will be classified in study phases according to [Table 3](#).

Assessments/events are assigned to study phases sequentially, starting from the top of each table.

**Table 3 Assignment of Study Phases**

For All Events or Assessments	
Study Period	Date range
Screen	If actual “Time of Day” for the assessment/event is collected: Start Date and Time < OLI Treatment Start Date & Time
	If actual “Time of Day” for the assessment/event is not collected:
	Start Date < OLI Treatment Start Date
OLI Phase	If actual “Time of Day” for the assessment/event is collected: For participants continuing into Injection Phase: OLI Treatment Start Date & Time ≤ Start Date & Time < Date & Time of CAB + RPV Injection
	For participants not continuing into Injection Phase: OLI Treatment Start Date & Time ≤ Start Date & Time
	If actual “Time of Day” for the assessment/event is not collected:
	For participants continuing into Injection Phase: OLI Treatment Start Date ≤ Start Date < Date of CAB + RPV Injection
	For participants not continuing into Injection Phase: OLI Treatment Start Date ≤ Start Date
Injection Phase	If actual “Time of Day” for the assessment/event is collected: Date & Time of CAB + RPV Injection ≤ Start Date & Time and Start Date ≤ Date of Nominal Follow-up Week 4
	If actual “Time of Day” for the assessment/event is not collected:
	Date of CAB + RPV Injection ≤ Start Date ≤ Date of Nominal Follow-up Week 4 Visit
Follow-up Phase	Date of Nominal Follow-up Week 4 Visit < Start Date

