### **10.2. Sample Size Determination**

There was no formal calculation of power or sample size for this study. Approximately 15 participants will receive CAB LA + RPV LA IM injections and provide informative safety and pharmacokinetic data based on feasibility considerations.

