**Table 6 Baseline Parameter Specifications**

Phase	Parameter	Study Assessments Considered as Baseline	Baseline Used in Data Display
Oral Lead-in Phase	Laboratory results, Vital Sign results, ECG results 	OLI Baseline = last non-missing pre-dose assessment collected <= Date of first OLI dose	OLI Day 1
Injection Phase	Laboratory results, Vital Sign results (pre-dose), ECG results  (pre-dose), CCI scores	Injection Phase Baseline = assessment collected on the date of CAB + RPV injection	Injection Day 1
Follow-up Phase	Laboratory results, Vital Sign results (pre-dose), ECG results  (pre-dose)	Follow-up Phase Baseline = assessment collected on the date of CAB + RPV injection	Injection Day 1

1. Average of the triplicate assessments for quantitative assessments will be used as the baseline.

If time is not collected, Day 1 assessments are assumed to be taken prior to first dose of the respective phase. Unless otherwise stated, if baseline data is missing no derivation will be performed and baseline will be set to missing.

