## 11.2. Appendix 2: Assessment Windows

All assessments/events (including those from planned, unscheduled and withdrawal visits) will be assigned to assessment windows/analysis visits according to actual dates of collection rather than the nominal visit labels recorded on the eCRF or in the laboratory database. All assessment data, including unscheduled data will be presented in listings.

For parameters which are not scheduled to be assessed at a particular visit, the all-inclusive assessment windows will still be used; however, data displays summarizing measurements by visit will only report visits in which the parameter is a planned collection according to [Appendix 1: Schedule of Activities](#)

Note: Prior to visit slotting, assessments are first assigned to a study phase according to [Table 3](#).

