### 11.2.1. Definitions of Assessment Windows

**Table 8 Assessment Windows for Screening and OLI Phase Data**

Parameter	Analysis Window	Target Period Day	Analysis Timepoint
Assessments assigned to Phase=Screening or OLI (per Table 3)			
All	OLI Phase Day <1	The day of earliest record	Screening
PK, Vital Signs, Labs, ECG	OLI Phase Day = 1	1	Day 1
PK, Vital Signs, Labs	OLI Period Day = 2	2	Day 2
PK	13 ≤ OLI Phase Day ≤ 15	14	Day 14
Vital Signs, Labs	3 ≤ OLI Phase Day ≤ 21	14	Day 14
PK	28 ≤ OLI Phase Day ≤ 30	29	Day 29
Vital Signs, Labs, ECG	22 ≤ OLI Phase Day	29	Day 29
If none of the above			Day X, where X=OLI Phase day

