**Table 9 Assessment Windows for Injection & Follow-up Phase Data**

Parameter a	Analysis Window	Target Period Day	Analysis Timepoint
Assessments assigned to Phase=Injection (per Table 3)			
PK, Vital Signs, Labs, ECG, CCI	Injection Phase Day = 1	1	Day 1
PK, Vital Signs, CCI	Injection Phase Day = 2	2	Day 2
PK	Injection Phase Day = 4	4	Day 4
CCI	3 ≤ Injection Phase Day ≤ 4	4	Day 4
PK	Injection Phase Day = 5	5	Day 5
Vital Signs	3 ≤ Injection Phase Day ≤ 6	5	Day 5
CCI	5 ≤ Injection Phase Day ≤ 6	5	Day 5
ECG	2 ≤ Injection Phase Day	5	Day 5

Parameter a	Analysis Window	Target Period Day	Analysis Timepoint
PK	Injection Phase Day = 7	7	Day 7
PK	Injection Phase Day = 8	8	Day 8
CCI	7 ≤ Injection Phase Day	8	Day 8
Vital Signs	7 ≤ Injection Phase Day ≤ 9	8	Day 8
Labs	2 ≤ Injection Phase Day ≤ 10	8	Day 8
PK	Injection Phase Day = 10	10	Day 10
Vitals	10 ≤ Injection Phase Day ≤ 12	10	Day 10
PK	Injection Phase Day = 15	14	Day 15
Vital Signs	12 ≤ Injection Phase Day ≤ 16	14	Day 15
PK	Injection Phase Day = 17	17	Day 17
Vital Signs	17 ≤ Injection Phase Day ≤ 19	17	Day 17
Labs	11 ≤ Injection Phase Day ≤ 23	17	Day 17
PK	Injection Phase Day = 22	22	Day 22
Vital Signs	20 ≤ Injection Phase Day ≤ 25	22	Day 22
PK	Injection Phase Day = 28	28	Week 4
Vital Signs	26 ≤ Injection Phase Day	28	Week 4
Labs	24 ≤ Injection Phase Day	28	Week 4
	If none of the above		Day X, where X=Injection Phase Day
Assessments assigned to Phase=Follow-up (per Table 3)			
Vital Signs, Labs	(Date of Nominal Follow-up Week 4 Visit – CAB + RPV Injection Date) +2 ≤ Injection Phase Day ≤ 70	56	Week 8
PK	53 ≤ Follow-up Period Day ≤ 59	56	Week 8
Vital Signs, Labs	71 ≤ Follow-up Period Day ≤ 126	84	Week 12
PK	81 ≤ Follow-up Period Day ≤ 87	84	Week 12
Vital Signs, Labs	127 ≤ Follow-up Period Day ≤ 210	168	Week 24
PK	165 ≤ Follow-up Period Day ≤ 171	168	Week 24
Vital Signs, Labs	211 ≤ Follow-up Period Day ≤ 308	252	Week 36
PK	249 ≤ Follow-up Period Day ≤ 255	252	Week 36
Vital Signs, Labs, ECG	309 ≤ Follow-up Period Day	364	Week 52
PK	361 ≤ Follow-up Period Day ≤ 367	364	Week 52
	If none of the above		Day X, where X=Follow-up Phase Day
NOTES:			

 
OLI Day, Injection Day, and Follow-up Day are defined in Section 11.5.1.
 
			

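### Timed pre-injection vital signs, and off-drug early-withdrawal vital signs and labs, are slotted to the oral lead-in 'Day 29' visit; for the pre-injection records this conflicts with SAP Table 6

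*SAP*

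**What the plan says.** - **Order of operations.** SAP Appendix 2 (11.2) slots records by actual collection date, not by the eCRF visit label, and before slotting "assessments are first assigned to a study phase according to" Table 3. Section 11.3.1 adds: "Assessments/events are assigned to study phases sequentially, starting from the top of each table".
- **Phase boundary (Table 3, Assignment of Study Phases).** For injected participants, OLI runs up to, but not including, "Date & Time of CAB + RPV Injection" if a time of day is collected. If not, it runs up to, but not including, "Date of CAB + RPV Injection". For participants who are never injected, OLI has no end under either rule.
- **OLI windows (Table 8).** Vital signs, labs and ECG go to Day 29 when "22 ≤ OLI Phase Day", with target day 29 and no upper limit. The PK window for Day 29 is closed at Days 28 to 30. The table draws on Screening and OLI records together.
- **Injection windows (Table 9).** The source is "Assessments assigned to Phase=Injection" only.
- **Baseline (Table 6).** "Injection Phase Baseline = assessment collected on the date of CAB + RPV injection", marked pre-dose for vital signs and ECG and displayed as Injection Day 1. The same baseline serves the Follow-up phase.
- **Several records in one window (11.5.1).** The one nearest the target day is summarised by visit. All valid records count in summaries across visits, such as maximum grade.
- **Visits.** The schedule requires ECG and vital signs to be checked before injection on Day 1. A participant withdrawn before injection has a visit 10 to 14 days after the last oral dose, with vital signs and labs. Section 11.6.1 slots withdrawal visits by Appendix 2.

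**The concern.** Read in sequence, these rules never let a timed pre-injection reading reach the visit that Table 6 names for it. The reading leaves the Injection phase at the first step and is picked up by an OLI window that was left open. On the oral side the same situation is harmless, because Table 8 pools Screening with OLI. Table 9 has no matching provision, which suggests an oversight rather than a choice.

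The by-visit safety displays are at stake. The Injection Day 1 row would lack its pre-dose values. In some participants a value taken after washout would be shown as the end of 28 days of oral dosing. For liver chemistry that label matters: the protocol's risk table (2.3.1) says all suspected drug-induced liver injury so far arose on oral cabotegravir.

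**Working it through.** There is no planning figure to reproduce: "There was no formal calculation of power or sample size for this study". The check applies the stated rules to dated records.

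**1. OLI day of the injection.** By 11.5.1, phase day = assessment date − first oral dose date + 1, so the last oral dose is on Day 28. Protocol 4.1.2 gives a washout of 10 to 14 days.
- Counted from the Day 28 dose: 28 + 10 = 38 to 28 + 14 = 42.
- Counted from the Day 29 visit: 29 + 10 = 39 to 29 + 14 = 43.

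Protocol Appendix 8 allows a longer washout with no stated limit. The day is always at least 22, and lies 38 − 29 = 9 to 43 − 29 = 14 days from the target.

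**2. Where each record goes.**

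| Record | Phase (Table 3) | Visit (Tables 8 and 9) |
|---|---|---|
| Injection date, timed, before injection: vital signs, labs, ECG | OLI | Day 29 |
| Injection date, timed, before injection: PK, if sampled | OLI | Day X, X = 38 to 43 |
| Injection date, untimed | Injection | Injection Day 1 |
| Injection date, timed, after injection | Injection | Injection Day 1 |
| OLI Day 1, timed, before first oral dose | Screen | Day 1 (phases pooled) |

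**3. Which parameters carry a time.** SAP 7.7 lists vital signs by actual date and time. It lists ECG by record date, and 7.6 lists labs by collection date. The first row of the table is therefore documented for vital signs and conditional for labs and ECG.

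**4. Which record is reported as Day 29 in an injected participant.** The rule is the smallest |day − 29|.
- Days 29 and 38: distances 0 and 9, so Day 29 is used.
- Days 22 and 38: distances 7 and 9, so Day 22 is used.
- Day 38 or Day 42 alone: that off-drug record is used.

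Any other record from Day 22 to Day 37 is at most 8 days from the target and wins. Substitution needs a timed pre-injection record and no nearer one.

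**5. Early withdrawal before injection.** With the last oral dose on Day L, the visit is on Day L + 10 to L + 14. It can reach Day 22 if L + 14 ≥ 22, so L ≥ 8. It always does if L + 10 ≥ 22, so L ≥ 12.

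| Last oral dose | Visit on OLI Day | Slot for vital signs and labs |
|---|---|---|
| Day 7 | 17 to 21 | Day 14 (window 3 to 21) |
| Day 8 | 18 to 22 | Day 14 or Day 29 |
| Day 12 | 22 to 26 | Day 29 |
| Day 20 | 30 to 34 | Day 29 |
| Day 28 | 38 to 42 | Day 29 |

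This does not depend on a time being collected. The value is the one summarised unless a nearer record exists.

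**6. How far off drug.** Protocol 4.2.1 equates 10 to 14 days with about 7 to 10 half-lives. Assuming first-order decline, 0.5^7 = 0.8% to 0.5^10 = 0.1% of the level remains.

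**7. How often.** The documents give no rate of missed Day 29 visits. As an illustration, if each of 15 participants misses it independently with probability 5%, 10% or 15%, the chance of at least one is 1 − (1 − p)^15 = 0.54, 0.79 or 0.91. One participant is 1/15 = 6.7% of such a row.

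**The case against.** The strongest defence is that the baseline value is safe. Table 6 defines it by injection date, section 5.2 asks for the latest reading before dosing, 7.7 takes the mean of pre-dose ECG triplicates, and 11.5.1 subtracts the baseline so defined rather than a visit row. This stands. A reader might infer that the injection baseline is lost and change from baseline is wrong; the documents do not support that. The conflict concerns the phase, the visit label and the displayed row.

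Three other strong readings also fail.
- **Labs and ECG misplaced in every injected participant.** No collection time is documented for either, and untimed records slot correctly. Labs are also absent from the schedule's list of pre-injection checks.
- **Off-drug values generally replacing Day 29.** The nearest-to-target rule protects a real Day 29 record.
- **Damage to the primary endpoint.** The injection schedule is too broken in the text to show a pre-dose PK sample. If there is one, it goes to Day X, and 8.2 derives PK parameters from actual times.

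It is also fair that slotting withdrawal visits by window, and counting washout safety events with OLI (5.1), are deliberate. That does not explain why a measurement 10 to 14 days after the last dose should be labelled as the end-of-treatment visit, or why the pre-injection check should be.

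**Conclusion.** The rules as written are inconsistent and should be corrected, at a limited size.

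- **Pre-injection records.** Tables 3, 8 and 9 put timed vital signs under OLI Day 29, while Table 6 shows them as Injection Day 1. This affects all of the roughly 15 injected participants for vital signs, and labs or ECG only if times are collected. A timed post-injection reading, if one is scheduled, would fill the Injection Day 1 row instead. These pre-injection records also count in OLI worst-case and maximum-grade summaries, even where a real Day 29 record exists.
- **Early withdrawals.** Vital signs and labs go to Day 29 for any uninjected participant whose last oral dose was on Day 12 or later, and possibly from Day 8, whether or not times are collected.
- **Missed Day 29.** An off-drug value stands in only for an injected participant with a timed pre-injection record and nothing nearer.

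The number of participants in the last two groups cannot be known from the documents. The effect is confined to by-visit and by-phase safety displays. The conclusion assumes the tables are programmed literally; a programmer who noticed the clash would have to choose a rule that the SAP does not state.

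**What to change.** 1. State in both Table 3 and Table 9 that injection-date records before the injection time are slotted to Injection Day 1 (pre-dose). This gives the result that Table 8 already achieves for OLI Day 1 by pooling phases. Changing Table 9 alone would leave Table 3 contradicting it.
2. State which phase these records count in for worst-case and maximum-grade summaries.
3. Put an upper limit on the Table 8 Day 29 window for vital signs, labs and ECG that ends before washout is complete, so below Day 38; Day 22 to 31 would serve as an example.
4. Give post-treatment early-withdrawal visits their own label. The cap alone is not enough: a last dose on Day 12 gives a visit on Days 22 to 26, still inside a 22 to 31 window.

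The cost is a small reconciliation of SAP Appendices 2 and 3 with Table 6, and some programming. Appendix 9 describes the display list as tentative until the full plan is written, so the change can be made then. No data collection changes.

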**NOTES:**

- Date = Date of assessment

**Table 4 Study Phases for Concomitant Medication**

Concomitant during:	
Study Period	Date range
Prior	Medication Taken < OLI Treatment Start Date & Time
OLI Phase	For participants continuing into Injection Phase: OLI Treatment Start Date & Time ≤ Medication Taken < Injection Phase Treatment Start Date & Time  For participants not continuing into Injection Phase: OLI Treatment Start Date & Time ≤ Medication Taken
Injection Phase	Injection Phase Treatment Start Date & Time ≤ Medication Taken ≤ Date of Nominal Follow-up Week 4 Visit
Follow-Up Phase	Date of Nominal Follow-up Week 4 Visit < Medication Taken

**NOTES:**

- If concomitant medication time is missing, the medication will be assumed to be taken predose, prior to that day's treatment dosing.
- Please refer to Appendix 6: Reporting Standards for Missing Data. for handling of missing and partial dates for concomitant medication. Use the rules in this table if concomitant medication date is completely missing.

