Injection Site Reactions (ISR)	
There are extensive safety and tolerability data, including ISRs following IM administration of CAB LA and RPV LA. Please refer to each IB for additional information [CAB IB GlaxoSmithKline Document Number RH2009/00003/09, RPV IB, 2019]
	
 
Administration advice to minimize risk of poor administration technique giving rise to injection site reactions. Advice on care, monitoring, natural course, and treatment of ISRs given in study documentation
 
Advice to participants on care of injection site on day/days immediately post administration, use of analgesia, compresses where appropriate.
 
Participants will be closely monitored for ISRs particularly for signs of pain, tenderness, infections, erythema, swelling, induration, or nodules (granulomas or cysts) throughout the study.
 
Complications of ISRs such as infections (abscess, cellulitis) and
 

Potential Risk of Clinical Significance	Summary of Data/Rationale for Risk	Mitigation Strategy
		
collections of fluid requiring drainage will be monitored
 
 
Significant ISRs may be photographed and referred to a dermatologist for specialist advice.
 

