#### **6.2.1. Dosing Considerations for CAB LA + RPV LA**

Vials of CAB LA and RPV LA are each supplied as a suspension and need no further dilution or reconstitution. Since RPV LA requires refrigeration, sites should allow the vial(s) to come to approximately room temperature prior to injecting. The vials should be gently inverted a few times to re-suspend sediments and allow bubbles to subside, and then use a syringe or provided vial adapter to withdraw the required volume of suspension for IM injection.

All injections must be given intramuscularly in the thigh muscle, each injection on one thigh. The time and location of injection will be captured in the case report form (CRF).

Additional injections instructions can be found in the SRM.

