#### **6.4. Concomitant Therapy**

Any medication or vaccine (including over-the-counter or prescription medicines, vitamins, and/or herbal supplements or other specific categories of interest) that the

participant is receiving at the time of enrollment or receives during the study must be recorded along with:

- reason for use
- dates of administration including start and end dates
- dosage information including dose and frequency

The Medical Monitor should be contacted if there are any questions regarding concomitant or prior therapy.

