#### **6.4.1. Permitted Medications and Non-Drug Therapies**

Participants must abstain from taking prescription drugs within 7 days (or 14 days if the drug is a potential enzyme inducer) or 5 half-lives (whichever is longer) before the start of study intervention until completion of the follow-up visit, unless, in the opinion of the investigator and sponsor, the medication will not interfere with the study.

Participants must abstain from taking non-prescription drugs (including vitamins and dietary or herbal supplements) within 7 days (or 14 days if the drug is a potential enzyme inducer) or 5 half-lives (whichever is longer) before the start of study intervention until the last PK sample collected on Week 8, unless, in the opinion of the investigator and sponsor, the medication will not interfere with the study.

Paracetamol/Acetaminophen at doses of  $\leq$  2 grams/day is permitted for use any time during the study. Other concomitant medication may be considered on a case-by-case basis by the investigator in consultation with the Medical Monitor if required.

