### 11.9.3. Study Population Tables

Study Population Tables					
No.	Population	GSK Standard / Example Shell	Title	Programming Notes	Deliverable [Priority]
Subject Disposition					
1.1.	Safety	ES1	Summary of Subject Disposition for the Subject Conclusion Record	ICH E3, FDAAA, EudraCT	SAC
1.2.	Safety	DISP_T1	Summary of Subject Disposition at Each Study Phase	ICH E3	SAC
1.3.	Safety	DISP_T2	Summary of Reasons for Withdrawal at Each Study Phase		SAC
1.4.	Screened	ES6	Summary of Screening Status and Reasons for Screen Failure	Journal Requirements	SAC
Protocol Deviation					
1.5.	Safety	DV1	Summary of Important Protocol Deviations by Study Phase and Overall	ICH E3	SAC
Population Analysed					
1.6.	Enrolled	SP1	Summary of Study Populations by Study Phase and Overall	GSK Statistical Display Standard Note: Show n's at each study phase.	SAC
Demographic and Baseline Characteristics					
1.7.	Safety	DM1	Summary of Demographics and Baseline Characteristics	ICH E3, FDAAA, EudraCT Note: To include Age Ranges	SAC
1.8.	Safety	DM5	Summary of Race and Racial Combinations	ICH E3, FDA, FDAAA, EudraCT	SAC
Prior and Concomitant Medications					
1.9.	Safety	MH1	Summary of Past Medical Conditions	ICH E3	SAC
1.10.	Safety	CM1	Summary of Concomitant Medications by Study Phase and Overall	ICH E3	SAC

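### The SAP puts an untimed injection-day medication in the oral lead-in phase but an untimed injection-day adverse event in the Injection phase

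*SAP*

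**What the plan says.** **What is recorded.** Protocol 6.4 asks, for each concomitant medication, for the reason for use, "dates of administration including start and end dates", and the dose and frequency. A clock time is not on the list. For the injection itself, Protocol 6.2.1 does require the time to be captured.

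**How medications are assigned to phases.** In SAP Appendix 3 Table 4 (Study Phases for Concomitant Medication), the lower bound of the Injection phase is "Injection Phase Treatment Start Date & Time ≤" the medication. Anything from the first oral dose up to that moment is OLI, which therefore includes the washout. Anything before the first oral dose is Prior. The note to the table adds: "If concomitant medication time is missing, the medication will be assumed to be taken predose, prior to that day's treatment dosing".

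**How adverse events are assigned.** In SAP Appendix 3 Table 3 (Assignment of Study Phases), the Injection-phase rule for a record whose time of day is not collected is "Date of CAB + RPV Injection ≤ Start Date ≤ Date of Nominal Follow-up Week 4 Visit". An event dated on the injection day is thus an Injection-phase event. An untimed event dated on OLI Day 1 is likewise an OLI event.

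**Where it is reported.** SAP Table 1.10 is titled "Summary of Concomitant Medications by Study Phase and Overall", and Listing 29 lists the same records by phase.

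**Whether same-day analgesia is foreseen.** The injection site reaction entry in Protocol 2.3.1 includes advice to participants on "use of analgesia, compresses where appropriate", covering the injection day and the days just after it. Protocol 6.4.1 says that paracetamol, within its stated limit, "is permitted for use any time during the study".

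**The concern.** Two tables in one SAP appendix use opposite defaults for a date-only record on a dosing day, and no reason is given. Assuming that an untimed record precedes the dose is sensible for a scheduled pre-dose assessment. It is a poor assumption for an as-needed medicine taken because of that day's injection.

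The study looks at tolerability at a new injection site. A reader may well use the phase columns of Table 1.10 to see how much symptomatic treatment followed the injection. Under the present note, an untimed analgesic taken only on that day leaves the Injection column and appears in OLI, at a point when the participant had been in washout for 10 to 14 days. At the other boundary, an untimed medicine taken on OLI Day 1 for an early symptom becomes a prior medication.

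**Working it through.** The documents give no figure to reproduce. The check is to trace date-only records through the two tables.

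**Inputs.** Boundary for medications: SAP Appendix 3 Table 4. Default for a missing time: the note to Table 4. Boundary for untimed events: SAP Appendix 3 Table 3. Number injected: about 15 (Protocol 10.2). Illustrative clock times, not from the documents: injection 09:00, pain 13:00, analgesic 14:00 on the same day.

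**Step 1: the ordering.** The injection time is captured. A medication deemed taken before the dose therefore always sorts ahead of the injection on that date, and Table 4 returns OLI.

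**Step 2: the cases.** Table 4 does not say whether its medication term means the start of use or the whole period of use, so both readings are shown where they differ.

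| Record | Time recorded? | Phase under present rules | Phase with Table 3's default |
|---|---|---|---|
| Pain on injection day | yes or no | Injection | Injection |
| Analgesic, injection day only | no | OLI | Injection |
| Analgesic, injection day to Day 3 | no | OLI (start-date reading); OLI and Injection (interval reading) | Injection |
| Analgesic, injection day only | yes, 14:00 | Injection | Injection |
| Analgesic first taken on Day 2 | no | Injection | Injection |
| Medication, OLI Day 1 only | no | Prior | OLI |

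The pain and its same-day treatment separate only when the medication starts on the injection day and has no time. Records with a time, and medications first taken on a later day, are classified correctly already.

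**Step 3: size.** Let *k* be the number of participants whose only analgesic use in the phase is on the injection day and untimed. Taking 15 as the Injection-column denominator, the column is understated by 100 × *k*/15 percentage points, and OLI shows up to *k* users who do not belong there. One participant is 100 × 1/15 = 6.7 points. The documents do not give *k*, so the range is an assumption:

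- *k* = 0: 0.0%
- *k* = 3: 20.0%
- *k* = 8: 53.3%
- *k* = 15: 100.0%

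On the interval reading, a longer course stays in the Injection column and is counted in OLI as well. On the start-date reading it moves wholly to OLI.

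**The case against.** The strongest reply is that the note may rarely apply. A reader might infer from Protocol 6.4 that only dates are collected, so that nearly every record falls under the note. The documents do not show this. Protocol 6.4 lists what must be recorded and does not exclude a time, and the eCRF is not among the documents. The SAP's own wording leaves room for a time field: Table 4 compares medications with a date and time, and the note speaks of a time that is missing, whereas Table 3 has a branch for times that are not collected. This part of the reply stands. How often the note applies is unknown.

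Second, a reader might infer that the tolerability results are distorted. They are not. Injection site reactions are reported in Tables 3.20 to 3.22 and Listing 30 by treatment, and those counts do not use the medication rule. The diary listing (shell HO_03) shows home treatment, including paracetamol and compresses, by injection side and study day. PK analyses are untouched. Table 1.10 is a study population table, and concomitant medication is not among the visible endpoints. An injection-day record also stays in the Overall column and in Listing 29, although with the wrong phase. All of this stands and limits the consequence, but none of it corrects Table 1.10.

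Third, same-day analgesic use is foreseen but not quantified. The advice in Protocol 2.3.1 is conditional, and the Day 1 entries in the diary shell are mock data. No particular count can be claimed.

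**Conclusion.** The inconsistency is real and follows from the text alone. An untimed medication dated on the injection day goes to OLI, while an untimed adverse event on the same date goes to the Injection phase. The same split occurs at OLI Day 1, where the medication becomes Prior and the event OLI.

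The effect is confined to the phase attribution of untimed dosing-day medications in Table 1.10 and Listing 29 (and, at OLI Day 1, to their classification as prior rather than concomitant). Use on the injection day only moves wholly to OLI. A longer course is counted in OLI only or in both phases, depending on a reading that the SAP leaves open. Between 0 and about 15 participants could be affected, at 6.7 percentage points each. That range assumes a denominator of 15 and rests on an unknown frequency of missing times and same-day use. The documents do not support saying that most records are affected, or that the Injection column would show no analgesic use.

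This is a modest defect in a secondary display. It is worth correcting because the present default is least plausible for the very medicines a reader would look for on that day.

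**What to change.** Replace the note to SAP Appendix 3 Table 4 with:

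*If the medication time is missing and its start date equals the OLI Day 1 or injection date, assign it to the phase that starts that day, as Table 3 does for untimed adverse events, unless the record shows it was taken before dosing.*

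In the same place, state whether the medication term in Table 4 means the start date or the whole period of use, so that a course crossing the boundary is counted in one defined way.

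Do not go further and assign a medication to the phase of the adverse event it treats. That would let the event's phase override the medication's own date: a medicine taken in Follow-up for an event that began in OLI would be reported in OLI. On the injection day itself it could contradict the sentence above.

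The cost is one or two sentences and no new data. SAP Appendix 9 describes the display list as tentative until the full plan is written, so the change can be made then. The downside is that an occasional untimed medication actually taken before dosing on that day is counted in the phase that starts that day.
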